12.2.5 Percentage Change in Uterine Fibroid Volume by MRI

The percent change from baseline in total uterine fibroid volume will be determined at the end of treatment. This study will assess up to 3 fibroids present at baseline in each subject. The volume of these 3 fibroids will be summed to determine the total uterine fibroid volume at each assessment.

Within group paired tests will be used to assess treatment effect. Nonparametric methods will be employed as appropriate. If data are missing, a last observation carried forward procedure will be used, including the baseline, if necessary.

12.3 General Statistical Issues

A Statistical Analysis Plan (SAP) will be finalized prior to unblinding the study. For the efficacy variables a last observation forward approach will be used to impute missing data to generate a complete ITT data. If there are no post-baseline efficacy data then a value of no change will be imputed for the

missing efficacy measure. Statistical significance will be declared if the twosided p-value is ≤ 0.05 .

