7. TRIAL OBJECTIVES AND PURPOSE

[figure not shown]
The primary objective of this study is to determine the safety of orally administered Proellex administered at 12 mg/day for up to 3 courses of treatment (18 weeks each), each separated by an Off-Drug Interval (ODI), to women who have completed either ZPV-201 or ZPU-203.

To further investigate the effect of the timing of start of dosing upon the onset of amenorrhea, at selected sites the start of dosing in each cycle will be on the first day of bleeding rather than 0-4 days after stopping bleeding.

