12.2 Statistical and Analytical Plan

Analyses in this study will focus on comparison to two baseline assessments. One baseline is associated with the original parent study baseline and the other is associated with the 28-day period prior to the start of this extension study. Reference to baseline in this section refers to each baseline definition.

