12.2.3 Percentage Change in PBAC Scores

The percentage change in PBAC scores over each 28 day period of the course will be recorded and compared to baseline to determine onset of benefit. Additionally PBAC scores will be used to monitor the level of vaginal bleeding during the ODI.

Within treatment group paired t-tests will evaluate treatment effect. While the primary assessment will be after each 18 week treatment course, summaries will be prepared for each of the other visits. If data are missing, a last observation carried forward procedure will be used, including the baseline, if necessary. Non-parametric methods will be employed as appropriate.

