12.2.4 Percentage Change in Total and Individual Symptom Severity Scores for the UFSQOL

The UFSQOL has been validated as a three month look back

questionnaire. The survey will be administered at baseline and at the end of each course. Within group paired tests will be used to assess treatment effect. Non-parametric methods will be employed as appropriate. If data are missing, a last observation carried forward procedure will be used, including the baseline, if necessary.

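### Section 12.3 allows significance to be declared at 0.05 for each of at least 14 within-group efficacy tests, and no endpoint, baseline or course is designated for formal inference

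*Combined protocol and SAP*

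**What the plan says.** Section 12.3 (General Statistical Issues) gives the decision rule: "Statistical significance will be declared if the twosided p-value is" at most 0.05. It is not tied to any particular endpoint, and the available text contains no hierarchy, split of alpha or multiplicity adjustment.

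Section 12.2 doubles each comparison with baseline. It states "Analyses in this study will focus on comparison to two baseline assessments", namely the parent-study baseline and the 28 days before the extension, and adds "Reference to baseline in this section refers to each baseline definition".

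The efficacy subsections then set the tests:

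- **PBAC (12.2.3):** "Within treatment group paired t-tests will evaluate treatment effect", and "While the primary assessment will be after each 18 week treatment course, summaries will be prepared for each of the other visits".
- **UFSQOL (12.2.4):** "The survey will be administered at baseline and at the end of each course", with within-group paired tests on total and individual scores.
- **MRI fibroid volume (12.2.5):** percent change at the end of treatment, again with within-group paired tests.
- **Amenorrhea (12.2.2):** percentages only, with no test.

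Section 7 makes safety the primary objective, with dosing "for up to 3 courses of treatment (18 weeks each". Section 12.1 expects no more than 60 subjects and gives no power calculation. Section 12.3 also says that a separate SAP is still to be finalized.

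**The concern.** A rule that significance will be declared has force only if the reader knows which test carries the claim. Here one threshold covers every combination of endpoint, course and baseline. The report could feature whichever baseline or course gave a p-value below 0.05 and still follow the plan. The study is open-label, so results can be seen as they accrue and the choice could be made with data in view.

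What is at stake is how the efficacy results are presented. A declared significant change in an uncontrolled extension is easily read as a confirmed effect. The safety objective is not affected.

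**Working it through.** **Plan's own figure.** The only stated figure is the threshold of 0.05 per test. One test at 0.05 has a 5% error rate, so there is nothing further to reproduce: no family-wise rate, power or sample-size formula is given.

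**Count of tests** (time points × baselines):

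| Endpoint | Section | Time points | Baselines | Tests | Called primary? |
|---|---|---|---|---|---|
| PBAC | 12.2.3 | 3 | 2 | 6 | yes |
| UFSQOL total score | 12.2.4 | 3 | 2 | 6 | no |
| MRI fibroid volume | 12.2.5 | 1 | 2 | 2 | no |
| Amenorrhea | 12.2.2 | – | – | 0 | no |
| **Total** | | | | **14** | |

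Fourteen is a minimum. The individual UFSQOL scores add tests, but Section 12.2 does not say how many. PBAC over each 28-day period is also compared with baseline, but it is not clear that a test is meant, so those comparisons are not counted.

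**Chance of at least one false declaration if all nulls are true.**

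*Independent tests,* 1 − 0.95^k:

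- k = 6: 1 − 0.95^6 = 26.5%
- k = 14: 1 − 0.95^14 = 51.2%

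Whatever the dependence, the sum 0.05 × k is a ceiling: 30% and 70%.

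*Correlated tests.* The tests share subjects, baselines and follow-up values, so independence is unrealistic. The documents give no correlations, so these are assumed. With equally correlated normal test statistics:

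| Correlation between tests | 6 tests | 14 tests |
|---|---|---|
| 0.5 | 20.7% | 34.8% |
| 0.8 | 13.9% | 19.7% |

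*Second model.* A simulation of the 14 paired t-tests themselves (n = 60) set correlations between measurements instead. Those between follow-up values ran from 0.5 to 0.95. It gave about 22% down to 9% for the PBAC tests and 44% down to 21% for all 14. In that model change scores on different endpoints are uncorrelated, which keeps the 14-test figures higher.

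**If some effects are real.** A true effect cannot produce a false rejection of no change. If PBAC truly falls against both baselines, 14 − 6 = 8 tests remain: 1 − 0.95^8 = 34% under independence. If the 3 + 1 = 4 UFSQOL and MRI tests against the parent baseline also reflect real change, 4 remain: 1 − 0.95^4 = 19% under independence. Both fall further with positive correlation.

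**The case against.** The strongest reply is that this is a single-arm, open-label safety extension of about 60 subjects. No confirmatory efficacy claim depends on these tests. Without a control, a significant within-group change would not establish a treatment effect even with perfect control of alpha. That stands, and it is why the point carries little weight. It does not explain why the plan needs a rule for declaring significance at all.

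Section 12.2.3 also offers a partial hierarchy, since it separates the end-of-course PBAC assessments from other visits, which only get summaries. That is true, but six tests remain with no course or baseline chosen. The pending SAP may settle the matter; the available text does not show that it will.

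A reader might infer four stronger things, none of which the documents support:

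- *That the plan's 5% error rate fails.* The 0.05 is a per-test threshold. It holds for each test, and no family-wise rate is promised.
- *That the primary time points generate all 14 tests.* They belong to PBAC alone and give 6. The other 8 come from endpoints not called primary.
- *That 51% is the actual risk.* It assumes independence and no change on any endpoint against either baseline. Section 6.1 reports consistent induction of amenorrhea from 3 mg daily, and this study gives 12 mg, so no change in PBAC is not the likeliest case. Carrying the last observation forward also copies values across courses and would tend to raise correlation.
- *That change from the extension baseline is expected to be small.* Nothing says so. Under the main schedule in Section 8.2.1, Course 1 follows a menses, so the preceding 28 days would ordinarily include off-drug bleeding. For PBAC a large change is just as plausible.

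**Conclusion.** The point holds as a gap in specification. At least 14 within-group tests fall under one rule for declaring significance, and no single endpoint, baseline or course is designated to carry a formal conclusion.

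Under the global null and assumed equal correlations of 0.8 to 0.5, the size is 14–21% for the PBAC tests and 20–35% for all 14. The rate exceeded 5% in every global-null scenario tried, including the second model. These figures depend on assumed correlations and on all nulls being true, so they show the order of magnitude and do not predict the study's error rate.

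This is a cheap improvement of minor weight.

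**What to change.** Replace the significance sentence in Section 12.3 with: *Efficacy results are reported as estimates with 95% confidence intervals; p-values are nominal and no statistical significance is declared.* The paired tests in Section 12.2 can stay as they are under that label.

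If the sponsor wants one formal efficacy statement, name one endpoint, one baseline and one course in the protocol now, test that at 0.05, and keep everything else descriptive.

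The cost is one sentence. Data collection, sample size and procedures do not change. The sponsor gives up declared significance for secondary efficacy results, or for all but one of them under the second option.

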13. ETHICS

13.1 Subject Information and Consent

A properly executed, written informed consent in compliance with Food and Drug Administration (FDA) regulations and Good Clinical Practice (GCP) guidelines will be obtained from each subject prior to entering the study or performing any unusual or non-routine procedure that involve a risk to the subject. The Principal Investigator will submit a copy of the informed consent document to the Institutional Review Board for review and approval before research subjects are enrolled. The Principal Investigator will provide a copy of the signed informed consent to the subject and the original will be maintained in the subject's medical record.

13.2 Institutional Review Board

The Principal Investigator will provide the Institutional Review Board with all requisite material, including a copy of the informed consent. The study will not be initiated until the IRB provides written approval of the protocol and the informed consent and until approved documents have been obtained by the Principal Investigator and copies received by the Sponsor. Appropriate reports on the progress of this study by the Principal Investigator will be made to the Institutional Review Board and the Sponsor in accordance with the applicable government regulations and in agreement with the policy established by the Sponsor.

13.3 Monitoring Case Report Forms

Repros Therapeutics Inc. or their designee will monitor all aspects of the study with respect to current GCP and standard operating procedures for compliance with applicable federal regulations. These individuals will have access to all records necessary to ensure integrity of the data and will periodically review progress of the study with the Principal Investigator.

13.4 Study Record Retention

In accordance with FDA regulations and GCP guidelines, all study-related documentation shall be retained by the Principal Investigator for a minimum of 2 years after FDA approval of telapristone acetate or clinical development has been terminated. At that time, the Principal Investigator will contact Repros Therapeutics Inc. regarding further disposition of the study records and comply with instructions.

13.5 Data Quality Assurance

All data recorded during the study will be available for audit against source data and for compliance with GCP and specific protocol requirements. Monitoring of the study progress and conduct will be ongoing. The Principal Investigator will be responsible for the following:

1. Monitoring study conduct to ensure that the rights of subjects are protected;

- 2. Monitoring study conduct to ensure trial compliance with GCP guidelines; and
- 3. Monitoring accuracy, completion and verification from source documents of study data.

13.6 Confidentiality

All information provided to the Principal Investigator by Repros Therapeutics Inc. or their designees including non-clinical data, protocols, CRFs and verbal and written information will be kept strictly confidential and confined to the clinical personnel involved in conducting the study. It is recognized that this information may be released in confidence to the IRB. In addition, no reports or information about the study or its progress will be provided to anyone not involved in the study other than to Repros Therapeutics Inc. or their designees or in confidence to the IRB, except if required by law.

13.7 Publications

Following completion of the study, the data from the entire study or from subsets of the study may be considered for reporting at a scientific meeting or for publication in a scientific journal, in which case Repros Therapeutics Inc. will be responsible for these activities and will work with the Principal Investigator to determine how the manuscript is written and edited, the number and order of authors, the publication to which it will be submitted and other related issues.

14. INVESTIGATOR'S STATEMENT

I have reviewed the ZPU-203EXT protocol and Investigator Brochure and agree to conduct this study as outlined in the protocol and in compliance with ICH/GCP Guidelines.

Investigator

Date

Printed name

Page 45 of 50

Page 47 of 50

99

Protocol Title:	An Open-Label Extension Study of 12 mg Proellex® (Telapristone Acetate) Administered Orally in the Treatment of Premenopausal Women with Confirmed Symptomatic Uterine Fibroids
Changes From:	From Original Protocol dated June 22, 2016 To: Protocol Amendment 1 dated July 13, 2016
Reason for Amendme	ent: To add a different start of dosing date for selected sites
Changes to Protocol:	Significant changes to the protocol are listed below.

SECTION	CHANGED FROM	CHANGED TO	REASON FOR CHANGE
PROTOCOL SYNOPSIS: Study Design and Duration of Treatment	The study requires 16 visits and is approximately 13 months in duration	Statement added: The study requires 16 visits and is approximately 13 months in duration (up to 15 months for selected sites).	Change in design to investigate change in start of
		At selected sites subjects will commence dosing on the first day of bleeding in their next menstrual cycle after Visit 19 or Visit 24 (about 3 weeks after V19 or 24). The start of the second and third courses of treatment will start on the first day of bleeding in the subject's second menses following withdrawal of study drug.	dosing
PROTOCOL SYNOPSIS Study Endpoints	• Changes in clinical laboratory results to values significantly outside of normal range	• Changes in clinical laboratory results	Corrections
	• Changes in liver function-to values outside the normal range	• Changes in liver function values	
	• Change in Endometrial thickness assessed using vaginal ultrasounds	• Endometrial thickness assessed using vaginal ultrasounds	
	• Changes in the endometrium over the	• Pathology of the endometrium assessed by biopsies .	

SECTION	CHANGED FROM	CHANGED TO	REASON FOR CHANGE
	course of the treatment and ODI period (half of the subjects will be assigned to biopsy on the last day of treatment and half will undergo a biopsy after recovery menses).		
PROTOCOL SYNOPSIS Statistical Methods	Continuous efficacy endpoints, such as the change from baseline in uterine tumor volumes will assess treatment effect using a within-group t-test or appropriate non-parametric technique. Other continuous efficacy variables will be treated similarly. The percentage of subjects becoming amenorrheic will be determined. Safety and tolerability will be assessed	Continuous efficacy endpoints, such as the change from baseline in uterine tumor volumes will assess treatment effect using a within-group t-test or appropriate non-parametric technique. The percentage of subjects becoming amenorrheic will be determined.	Corrections
7. TRIAL OBJECTIVES		Statement added: To further investigate the effect of the timing of	Change in design to

SECTION	CHANGED FROM	CHANGED TO	REASON FOR CHANGE
AND PURPOSE		start of dosing upon the onset of amenorrhea, at selected sites the start of dosing in each cycle will be on the first day of bleeding rather than 0-4 days after stopping bleeding.	investigate change in start of dosing
8. TRIAL DESIGN 8.1 Study Endpoints			Corrections
8.2.1 Overview of Study Design		Statement added:At selected sites subjects will commence dosing on the first day of bleeding in their next menstrual cycle after Visit 19 or Visit 24 (about 3 weeks after V19 or 24). The start of the second and third courses of treatment will start on the first day of bleeding in the subject's second menses following withdrawal of drug.	Change in design to investigate change in start of dosing

SECTION	CHANGED FROM	CHANGED TO	REASON FOR CHANGE
8.3.2 Exclusion Criteria	 Subject had a significant decrease in bone mineral density while participating in ZPV-201 or ZPU-203 (total hip or spine measurement decreased by 5% or more) 	• Subject had a significant decrease in bone mineral density while participating in ZPV-201 or ZPU-203 (total hip or spine measurement decreased by more than 5%)	Correction
-			

SECTION	CHANGED FROM	CHANGED TO	REASON FOR CHANGE

105

SECTION	CHANGED FROM	CHANGED TO	REASON FOR CHANGE

SECTION	CHANGED FROM	CHANGED TO	REASON FOR CHANGE
10.1.1 Reporting Adverse Experiences	After Visit 20, all SAEs and any adverse events that the investigator considers to be due to the study drug (e.g. hepatotoxicity) and not those considered to be due to withdrawal of the drug (e.g. vaginal bleeding), will be collected.		Correction
12. STATISTICAL METHODS 12.2 Statistical and Analytical Plan		Statement added: Analyses in this study will focus on comparison to two baseline assessments. One baseline is associated with the original parent study baseline and the other is associated with the 28-day period prior to the start of this extension study. Reference to baseline in this section refers to each baseline definition.	Clarification
12.2.2 Incidence of Amenorrhea	The percentage of subjects who become amenorrheic during the 28 days leading up to the last day of dosing in each course will be determined.	The percentage of subjects who become amenorrheic during the 28 days leading up to the last day of dosing in each course will be determined. The incidence of amenorrhea during the entire course and after the 11 th day of the course will also be investigated.	Clarification
12.2.3 Percentage Change in PBAC scores	The percentage change in PBAC scores over each 28 day period for each menstrual cycle will be recorded	The percentage change in PBAC scores over each 28 day period of the course will be recorded	Correction
	vaginal bleeding to determine duration		Correction

SECTION	CHANGED FROM	CHANGED TO	REASON FOR CHANGE
	of benefit during the five menstrual eycle follow-up after dosing Course 2. Within treatment group paired t-tests will evaluate treatment effect. Pairwise comparisons of the treatment groups will be made using a two-sample t test as well to compare the pooled Proellex doses to placebo. While the primary assessment will be after 18 week of treatment, summaries will be prepared for each of the other visits.	Within treatment group paired t-tests will evaluate treatment effect. While the primary assessment will be after each 18 week treatment course , summaries will be prepared for each of the other visits.	Correction
12.2.5 Percentage Change in Uterine Fibroid Volume by MRI	The percent change from baseline in total uterine fibroid volume will be determined at the end of each 18 week dosing course	The percent change from baseline in total uterine fibroid volume will be determined at the end of treatment	Correction

SECTION	CHANGED FROM	CHANGED TO	REASON FOR CHANGE
12.3 General Statistical Issues	A Statistical Analysis Plan (SAP) will be finalized prior to unblinding the study.	A Statistical Analysis Plan (SAP) will be finalized prior to database lock.	Correction
